4.2 Analysis Methods

4.2.1 Patient Disposition, Important Protocol Deviations and Analysis Sets

Patient disposition will be summarised for all patients providing written informed consent/assent (as relevant), by treatment group and overall. The number (n) and percentage (%) of patients will be presented for the following categories:

- Enrolled (number of patients only)
- Randomised/not randomised + reason
- Received study treatment/did not receive study treatment + reason
- Completed study treatment/did not complete study treatment + reason
- Completed study/prematurely discontinued study participation + reason

Patients prematurely discontinuing study treatment administration and/or study participation due to COVID-19 related reasons will be presented.

Reasons for not receiving the study treatment, for not completing study treatment, and for premature discontinuation of study participation will also be listed. The relative study day of premature discontinuation/withdrawal will also be presented. Patient disposition regards study participation, as well as study treatment impacted by COVID-19, will also be presented in patient data listings.

A flow diagram of patient disposition will be presented.

Patient enrolment will also be summarised by region, country and centre. The denominator for percentage (%) will be the total number of patients in the full analysis set, by treatment group and overall.

Important protocol deviations, including those protocol deviations related to COVID-19, will be summarised using the full analysis set (refer to Sections 2.1 and 2.2). Important protocol deviations will be finalised prior to database lock and routine study unblinding. The number (n) and percentage (%) of randomised patients with at least one important protocol deviation and within standardised important protocol deviation categories will be presented by treatment group and overall. Patients with important protocol deviations will also be listed.

The number (n) of patients included or excluded from each analysis set will be presented, including the reason(s) for exclusion from each analysis set. Patients can have one or more reasons for exclusion and will be counted in each category as relevant. Patients' assignment to the various analysis sets and reasons for exclusion will be presented in patient data listings.

Patients with identified treatment deviations (where planned study treatment assignment differs from actual study treatment received) and patients with unplanned emergency

unblinding of their blinded treatment code during the treatment period, will be identified in patient data listings. To note, in defining the PP analysis set, patients for whom the blind was broken during the double-blind randomised treatment period (emergency unblinding) introduce potential for bias in subsequent assessments. Should such patients be identified it will result in exclusion of the patients' data, in any analyses based on the PP analysis set, following the point of emergency unblinding, but will not necessarily lead to exclusion of such patients from the relevant analysis set, if otherwise valid.

The onset of the global COVID-19 pandemic potentially impacts a patient's ability to complete the study visits as initially planned per protocol. As such, the visit impacted by pandemic (VISITP) eCRF will be utilised to summarise, at a minimum, the number (n) and percentage (%) of patients in the full analysis set, by treatment group and overall:

- Number of visits impacted:
 - Partially completed
 - Fully completed
 - Delayed
 - Not done
- Reason for visit impact:
 - Patient decision
 - Pandemic-related logistic issue
 - Other/Specification
- Visit contact mode:
 - Remote-audio
 - Remote-video
 - In-clinic
 - Other/Specification

Patient visits (scheduled and unscheduled), identifying those visits impacted by COVID-19, will be presented, in patient data listings.

4.2.2 Demographic and Baseline Characteristics

With reference to the general principles and definitions detailed in Sections 2.1, 3.1 and 4.1.1, demographic and baseline characteristics will be summarised using FAS, by treatment group and overall.

Demographic summary includes presentation of:

- Age (years)at randomisation (Visit 2)

- Age group at randomisation (Visit 2):
 - < 12 years
 - ≥ 12 years
- Sex
- Race
- Ethnicity
- Country

In addition, summary of patient characteristics includes presentation of:

- Baseline height (cm)
- Baseline weight (kg)
- Baseline body mass index (BMI):
 - Calculated as the ratio of patient's baseline weight (kg) to the square of the patient's baseline height (m): $BMI (kg/m^2) = (weight [kg]) / (height [m]^2)$

Where:

Height is collected in cm and will be converted to meters prior to calculating BMI by dividing by 100.

Similarly, summary of additional patient characteristics at baseline includes presentation of:

- ECG
- Seated pulse (beats/min)
- Malaria
- Eye examination
- Transcranial doppler

Patients' history of SCD will be characterised by summary of the following as collected on the SCDHIS eCRF:

- SCD genotype (HbSS/HbSB Thalassaemia)
- SCD history of complications
- Age (years) at diagnosis of SCD: Calculated as follows:
 - Age (years) at diagnosis = $(date\ of\ diagnosis - date\ of\ birth + 1) / 365.25$
- Number of years since SCD diagnosis: Calculated as follows:
 - Number of years since SCD diagnosis = $(date\ of\ randomisation\ [Visit\ 2] - date\ of\ diagnosis + 1) / 365.25$

Similarly, patients' history of VOC events will be characterised by summary of the following as collected on the VOC eCRF:

- Number of VOC events in past 12 months relative to screening (Visit 1) and categorised as:
 - ≤ 1 VOC event in the last 12 months relative to screening (Visit 1)
 - ≥ 2 to ≤ 4 events in the last 12 months relative to screening (Visit 1)
 - > 4 VOC events in the last 12 months relative to screening (Visit 1)
- Primary setting for VOC treatment
- Duration (days) from start of the last prior VOC event (prior to randomisation [Visit 2]) to randomisation (Visit 2): Calculated as:
 - Duration (days) = (date of randomisation [Visit 2] – start date of last prior VOC event) + 1

For the handling of missing/partial date of birth, date of SCD diagnosis and for prior VOC events start and stop dates as captured on the VOC eCRF, refer to [Appendix D](#) Missing/Partial Dates for Date of Birth, Diagnosis of Sickle Cell Disease, Prior VOCs, and VOCs During the Study.

Demographic and baseline characteristics will be listed for all patients, (as defined in Section 2.1).

4.2.3 Past and Current Medical and Surgical History

Medical/relevant surgical history that occurred prior to screening (Visit 1) regardless of whether the condition is ongoing at the time of screening (Visit 1) will be summarised using FAS, by treatment group and overall (refer to Section 2.1). Medical/relevant surgical history will also be listed for all patients in patient data listings.

All medical/surgical history will be classified according to the latest version of the Medical Dictionary for Regulatory Activities (MedDRA).

Past medical history are those medical conditions/diseases which stopped prior to screening (Visit 1), while current medical records are those medical conditions/diseases that are still present or ongoing at the time of screening (Visit 1).

The number (n) and percentage (%) of FAS patients with any medical/surgical history (records) will be tabulated by MedDRA system organ class (SOC) and preferred term (PT). A patient will only be counted once within a particular SOC/PT, even if he/she has multiple conditions/diseases/surgeries in the same SOC/PT.

4.2.4 Prior, Concomitant, and Post-discontinuation Medications and Therapies

All medications will be coded using the latest AstraZeneca Drug Dictionary at the time of database lock and categorised as follows:

- Prior medication: Defined as those medications that were taken prior to the date of first dose of study treatment, regardless of whether medication use is ongoing.
- Concomitant medication: Defined as those medications taken at any time on or after the day of the first dose of study treatment up to and including the day of the last dose of study treatment, regardless of whether medication use is ongoing. A medication started prior to the first dose of study treatment that is ongoing at the time of first dose of study treatment will be identified as both prior and concomitant.
- Post-discontinuation medication: Defined as those medications started after the last dose of study treatment.

The handling of partial or missing medication dates is detailed in [Appendix C Missing/Partial Start and Stop Dates for Medications/Transfusions](#).

All medications will be classified as allowed/disallowed following a physician review (prior to database lock) of the database and separate tables will be presented by treatment group and overall for patients who take allowed/disallowed concomitant medications.

Summary tables will present the number (n) and percentage (%) of patients in the safety analysis set, using at least one medication by generic term within anatomical therapeutic chemical (ATC) classification. Patients will be counted once at each level of summarisation (ATC classification/generic term).

Prior, concomitant and post-discontinuation medications (allowed/disallowed) will be listed for all patients (as defined in Section 2.1). Medications administered due to COVID-19 confirmed/suspected AEs/SAEs will be identified utilising the *indication* variable on the CM eCRF, by means of the prefix “COVID-19” and will be listed in a separate patient data listing.

This study will evaluate ticagrelor efficacy and safety when added to standard of care treatments in SCD. Hence, patients are not withheld from any other treatments that may be used in SCD (e.g., hydroxyurea) during the study conduct, which is important considering the use of a placebo control group. Use of background standard of care, such as hydroxyurea, will be presented as follows:

- Number (n) and percentage (%) of patients in the FAS with background standard of care (regardless of type), as captured on the CM eCRF, and confirmed as ongoing at randomisation (Visit 2), as relevant: This will be based on ATC codes: *L01XX*, *A09AB*, *A05BA*, *A16AA* and *B06AX* as indicated by the study physician.
- Number (n) and percentage (%) of patients in the FAS with baseline hydroxyurea use (Yes/No) as assigned by IxRS.
- Number (n) and percentage (%) of patients in the FAS with stable hydroxyurea use for 3 months before enrolment in the study (screening [Visit 1]) and where stop date of hydroxyurea use is greater than randomisation (Visit 2)/date of first dose of study

treatment or is ongoing, as captured on the CM eCRF. This will be based on ATC code: *L01XX*.

- Number (n) and percentage (%) of patients in the FAS with hydroxyurea use started after randomisation (Visit 2)/date of first dose of study treatment and a duration of at least 6 months. Duration (months) will be derived as follows:
 - Duration (months) = (latest stop date of hydroxyurea use - earliest start date of hydroxyurea use [AFTER randomisation {Visit 2}]) + 1 (converted to months)

Where:

In case of ongoing medication use, study completion date or date of premature study discontinuation will be used to impute the latest stop date of hydroxyurea use in order to derive duration (months) within the context of the study course.

4.2.5 Study Treatment Exposure and Compliance

The following will be summarised by individual dose level (15 mg/30 mg/45 mg [per tablet count] bd) and overall dose level, by actual treatment group and overall, using the safety analysis set (refer to Section 2.1):

- Total study treatment exposure (days)
- Actual study treatment exposure (days)
- Number of study treatment interruptions, as reported by the investigator on the EX eCRF where *action taken with study drug* is indicated as “drug interrupted”
 - Main reason for study treatment interruption, as judged by the investigator, will be presented differentiating between COVID-19 related reasons and non-COVID-19 related reasons
- Total missed exposure days due to study treatment interruptions, as reported by the investigator on the EX eCRF where *action taken with study drug* is indicated as “drug interrupted”
 - Total missed exposure days due to COVID-19 related study treatment interruptions, as reported by the investigator on the EX eCRF where *action taken with study drug* is indicated as “drug interrupted”
- Total exposure years (across patients) based on total study treatment exposure (days)
- Study treatment compliance (%)
- Study treatment compliance (%) category:
 - < 80 %
 - ≥80 % to ≤120 %
 - >120 %
 - Missing

- COVID-19 related reason
- Non-COVID-19 related reason
- Weight (kg) versus dose level administration disagreement

Study treatment exposure and compliance will be based on the CSP weight-based specifications:

- ≥ 12 to ≤ 24 kg body weight: 15 mg dose level: 1 tablet of ticagrelor 15 mg or 1 tablet of placebo to match ticagrelor 15 mg twice daily
- > 24 to ≤ 48 kg body weight: 30 mg dose level: 2 tablets of ticagrelor 15 mg or 2 tablets of placebo to match ticagrelor 15 mg twice daily
- > 48 kg body weight: 45 mg dose level: 3 tablets of ticagrelor 15 mg or 3 tablets of placebo to match ticagrelor 15 mg twice daily

For patients with a weight increase exceeding 12.5% of the upper weight limit of the weight-band (≥ 27 kg and ≥ 54 kg, respectively), the dose will need to be increased according to the next weight-band. Decrease in dose level is not allowed and there will be no dose adjustments for decreasing weight.

The double-blind randomised treatment period comprises the following scheduled dispense/return visit intervals:

- Visit 2 (Week 0) to Visit 6 (3 Months)
- Visit 6 (3 Months) to Visit 9 (6 Months)
- Visit 9 (6 Months) to Visit 12 (9 Months)
- Visit 12 (9 Months) to Visit 15 (12 Months)
- Visit 15 (12 Months) to Next Scheduled In-clinic Visit/EOS^a

^a Only for patients completing the 24-month double-blind randomised treatment period or who are still ongoing within the double-blind randomised treatment period at the time of the CSED.

Study treatment dispense/return can, however, occur at any unscheduled timepoint within each of the scheduled dispense/return visit intervals and may also be impacted by COVID-19 with related reasons as captured on the drug accountability pandemic (DAP) eCRF.

Considering the aforementioned specifications, the following data handling conventions will therefore apply:

4.2.5.1 Study Treatment Exposure

Total duration of study treatment exposure (days) by dose level and overall dose level (includes missed exposure days due to study treatment interruptions):

- Exposure (days) = (date of last dose of double-blind randomised study treatment – date of first dose of double-blind randomised study treatment) + 1

Where:

Date of first dose of double-blind randomised study treatment equals:

- Variable: *Start date of study drug administration*: Based on the EX eCRF, earliest administration date, at or after randomisation (Visit 2), at a given dose level and for each dose level received.
- By overall dose level: Overall earliest of the aforementioned first dose of study treatment administration dates, over all dose levels received.

Date of last dose of double-blind randomised study treatment equals:

- Variable: *End date of study drug administration*: As captured on the EX eCRF and is the latest administration date, on or after randomisation (Visit 2), at a given dose level and for each dose level received regardless of temporary study treatment administration discontinuation (study treatment interruptions).
- By overall dose level: Overall latest of the aforementioned last dose of study treatment administration dates, over all dose levels received. Patients may prematurely discontinue study treatment administration whilst continuing with scheduled assessments in the double-blind randomised treatment period. DOSDISC eCRF collects the variable, *date subject discontinued IP*. This date should equal the overall date of last dose of study treatment as captured on the EX eCRF but can be used in conjunction with EX data to accurately identify the overall date of last study treatment administration over all dose levels received in the double-blind randomised treatment period.

Total exposure years (across patients in a given treatment group) is defined as the sum of total double-blind randomised study treatment exposure (days) by overall dose level, including missed exposure days due to study treatment interruptions, for all patients in a given treatment group and is expressed in years as follows:

- Total exposure years (across patients) = Sum of (total study treatment exposure [days] by overall dose level)/360

Where:

Year = 360 days. .

Actual study treatment exposure (days) by dose level and overall dose level follows the same approach, however excludes all missed exposure days due to study treatment interruptions.

For example, *Patient 1: 30 mg dose level*:

Total study treatment exposure (days) = 238 days (from 18 Apr 2019 to 11 Dec 2019)

Missed exposure days = 9 days (from 17 Nov 2019 to 25 Nov 2019) considering only the total number of missing exposure days due to study treatment interruptions (action taken with study drug on EX eCRF indicated as “drug interrupted”)

Actual study treatment exposure (days) = 238 – 9 = 229 days

	Dose	Unit	Formulation	Freq	Reason for Action	Start Date	End Date	Action Taken with Study Drug
1	30	mg	TABLET	BID	Adverse Event	2019-04-18	2019-11-16	Drug Interrupted
2	30	mg	TABLET	BID	Other	2019-11-26	2019-12-11	Dose Increased due to Weight Gain
3	45	mg	TABLET	BID		2019-12-12	ONGOING	

4.2.5.2 Study Treatment Compliance

Study treatment compliance (%) by dose level and overall dose level as based on actual study treatment exposure (days) (refer to Section 4.2.5.1):

- Compliance (%) = (actual tablets taken/expected tablets taken) × 100

Where:

– Actual tablets taken equals:

- Per kit IDs for a given dose level: Difference between total tablets dispensed and total tablets returned, regardless of temporary study treatment administration discontinuation (study treatment interruptions) and noting that tablets may be returned after the end of the dose level administration.
- By overall dose level: Sum of actual tablets taken over all dose levels received.

If tablets returned amount is missing for any/all kit IDs dispensed, both dose level and overall dose level actual tablets taken will be missing, ie, no imputation assumptions of tablets taken will be applied and as such study treatment compliance will be missing.

– Expected tablets taken equals:

- Expected tablets to be taken per last available weight (kg) at the time of study treatment administration (planned) is based on actual study treatment exposure

(days) excluding missed exposure days due to study treatment interruptions, by each dose level received:

- * 15 mg (>12 kg to ≤24 kg body weight): 1× 15 mg tablet bd: 2× actual study treatment exposure (days)
 - * 30 mg (>24 kg to ≤48 kg body weight): 2× 15 mg tablets bd: 4× actual study treatment exposure (days)
 - * 45 mg (>48 kg body weight): 3× 15 mg tablets bd: 6× actual study treatment exposure (days)
- By overall dose level: Sum of expected tablets taken over all dose levels received

In addition, study treatment compliance (%), as derived per the aforementioned, will be categorised as follows:

- < 80 %
- ≥80 % to ≤120 %
- >120 %
- Missing

Number (n) and percentage (%) of patients in the safety analysis set, per compliance category will be presented, by actual treatment group and overall. Percentage will be calculated relative to the total number of patients in the safety analysis set, by actual treatment group and overall. If, for at least 10 patients in total across the two treatment groups, compliance (%) cannot be calculated, the reason for missing compliance will be presented, if relevant, as:

- COVID-19 related reason
- Non-COVID-19 related reason

In addition to the aforementioned, weight (kg) versus dose level administration disagreement will be determined as follows:

Weight (kg) will be assessed every 6 months per the planned schedule of assessments. Weight (kg) (whether scheduled or unscheduled), as available at the start of study treatment administration at a given dose level, will be assessed in accordance with the CSP weight-based specifications and categorised as follows:

- Weight-based dose level agreement
- Weight-based dose level disagreement

The number (n) and percentage (%) of patients in the safety analysis set with weight-based dose level disagreement at any time over the course of the double-blind randomised treatment period and over all dose levels received will be presented. Percentage will be calculated

relative to the total number of patients in the safety analysis set, by actual treatment group and overall.

Details related to the administration of investigational product during the double-blind randomised treatment period will be presented in patient data listings.

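### SAP 4.2.5.2 ties expected tablets both to current weight and to dose level received; read by weight, a correctly dosed, fully adherent child could score as low as 50% or 67%

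*SAP*

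**What the plan says.** SAP 4.2.5.2 defines "Compliance (%) = (actual tablets taken/expected tablets taken) × 100". The numerator is tablets dispensed minus tablets returned, counted by kit within a dose level.

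The denominator rests on one sentence with two bases. It opens with weight: "Expected tablets to be taken per last available weight (kg) at the time of study treatment administration (planned"). It closes with dose level, multiplying by actual exposure in "days) excluding missed exposure days due to study treatment interruptions, by each dose level received". Three rows follow, one per dose level. The lowest is written as "15 mg (>12 kg to ≤24 kg body weight): 1× 15 mg tablet bd: 2× actual study treatment exposure (days"). The other two have the same form: the 30 mg row is tied to weights above 24 and up to 48 kg and counts 4 tablets a day, and the 45 mg row is tied to weights above 48 kg and counts 6.

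Results are then grouped as below 80%, 80% to 120%, above 120%, or missing.

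The dosing rule is in SAP 4.2.5. The dose goes up "For patients with a weight increase exceeding 12.5% of the upper weight limit of the weight-band", given there as 27 and 54 kg, and protocol 7.2.2 has the same two thresholds. SAP 4.2.5 adds: "Decrease in dose level is not allowed". The compliance rows repeat neither the 27/54 kg thresholds nor the bar on decreases.

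SAP 4.2.5.2 also plans a separate check of weight against dose level, using the weight on record when each dose level starts. Weight is scheduled every six months.

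**The concern.** A child who starts on 15 mg and grows to 25 kg, or starts on 30 mg and grows to 50 kg, stays on the starting level under the documents' own rule. By current weight, that child belongs in the next compliance row. The numerator then follows the dose level while the denominator follows weight, and a child who took every tablet looks non-compliant. A child whose weight falls into a lower band looks over-compliant.

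The design makes such cases possible. It enrols children aged 2 to under 18, with up to 24 months of planned follow-up, and any gradual growth towards a dose increase passes through 24 to 27 kg or 48 to 54 kg. The SAP does not say which basis prevails when weight and dose level differ, so two programmers could produce different compliance tables from the same data.

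**Working it through.** **Plan's own figures.** The worked example in SAP 4.2.5.1 has 30 mg from 18 Apr to 11 Dec 2019: (11 Dec − 18 Apr) + 1 = 238 days. The interruption of 17 to 25 Nov is 9 days, and 238 − 9 = 229. This matches the SAP. The dose thresholds also match: 24 × 1.125 = 27 and 48 × 1.125 = 54.

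**Inputs.** Expected tablets per day are 2, 4 and 6 (SAP 4.2.5.2). The rows are cut at 24 and 48 kg (SAP 4.2.5.2). The dose rises at 27 and 54 kg and never falls (SAP 4.2.5). The child takes every tablet and is dosed as the documents specify.

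**Daily score while weight and level differ**

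| Level and weight | Taken | Expected by weight | Score by weight | Score by dose level |
|---|---|---|---|---|
| 15 mg, >24 to <27 kg | 2 | 4 | 50.0% | 100% |
| 30 mg, >48 to <54 kg | 4 | 6 | 66.7% | 100% |
| 30 mg, fallen to ≤24 kg | 4 | 2 | 200% | 100% |
| 45 mg, fallen to ≤48 kg | 6 | 4 | 150% | 100% |

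For the SAP's example, the dose-level reading expects 4 × 229 = 916 tablets. Had that child weighed >48 to <54 kg throughout (an assumption, since the example gives no weights), the weight reading would expect 6 × 229 = 1374, and 916/1374 = 66.7%.

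**Part of exposure in the gap.** Let f be the share of counted exposure days spent in the gap.

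- 15 mg: 2 / [2(1 − f) + 4f] = 1/(1 + f). This is below 0.80 only if f > 0.25.
- 30 mg: 4 / [4(1 − f) + 6f] = 1/(1 + f/2). This is below 0.80 only if f > 0.50.

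**Assumed growth paths** (weights at 0, 6, 12 and 18 months, four equal intervals, weight reading):

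- 23.5, 25, 26, 27.5 kg: 15 mg level (2+2+2)/(2+4+4) = 60.0%; overall (6+4)/(10+4) = 71.4%.
- 21, 22.5, 23.5, 25 kg: 8/(2+2+2+4) = 80.0%.
- 46, 49, 52, 55 kg: 30 mg level (4+4+4)/(4+6+6) = 75.0%; overall (12+6)/(16+6) = 81.8%.
- 47, 50, 52, 53 kg: 16/(4+6+6+6) = 72.7%.
- 20, 21, 22, 23 kg, inside one band throughout: 100%.

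Under the dose-level reading every path gives 100%. The same holds if the row is chosen by weight at the start of each dose level.

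**The case against.** The strongest reply is that the calculation is really by dose level. Compliance is reported by dose level, the numerator is per kit within a level, the rows are labelled 15, 30 and 45 mg, and the overall figure sums over levels received. Exposure days are built per level from the EX eCRF. Using current weight would mean splitting days within a level by weight, and the SAP defines no such split. SAP 4.2.5 also states the 27/54 kg rule and the bar on decreases before introducing the conventions of 4.2.5.2, so the word *planned* can fairly be taken to include them. This is a reasonable reading, and it scores these children 100%. It does not remove the weight wording or the kg limits from the rows, and nothing says they give way.

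Three stronger inferences are tempting, and the documents support none of them:

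- **That growing children will be scored 50% to 67%.** One reading of an ambiguous sentence can do this, and those values are floors.
- **That the error reaches protocol deviations, the per-protocol set or the primary result.** The deviations listed in SAP 2.2 do not include a compliance percentage. The primary analysis in SAP 4.2.6.1 uses the full analysis set, and compliance is not in the model. The detailed per-protocol exclusion rules are in a separate plan that is not available here, so an effect there is unknown.
- **That it biases the comparison of arms.** Placebo tablets follow the same weight bands, so the documents give no reason to expect a difference between arms.

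**Conclusion.** The conflict is real and minor. SAP 4.2.5.2 states two bases for expected tablets, and they disagree for children held on a level outside their current weight band. On the weight reading, an adherent, correctly dosed child scores between 50% and 100% at the 15 mg level and between 67% and 100% at the 30 mg level when weight rises. That child enters the below-80% category only past the 25% or 50% share of exposure shown above. The bar on dose decreases does not cause low scores: it pushes them up after weight loss, to at most 200% at 30 mg or 150% at 45 mg. On the dose-level reading nothing is wrong.

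The sizes assume full adherence, correct dosing and days counted by the weight then on record. The growth paths are illustrative. The documents do not show how many children spend time in a gap, and SAP 3.1.4.1 records that the study stopped early, so follow-up may be shorter than the 24 months assumed. The effect shown is confined to the descriptive compliance table.

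**What to change.** In SAP 4.2.5.2, define expected tablets as 2, 4 or 6 per actual exposure day at the dose level assigned by IxRS and recorded on the EX eCRF. Delete the reference to last available weight and the kg bands from the compliance rows. Every adherent, correctly dosed child then scores 100%.

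Deleting the bands also removes a small mismatch: the 15 mg row begins above 12 kg, whereas SAP 4.2.5 and protocol 7.2.1 include 12 kg, so a child of exactly 12.0 kg fits no row.

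Keep weight for the separate agreement check, with a note that it uses weight only at the start of each dose level and so does not catch every later mismatch.

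The cost is one sentence, the deletions and the note. It needs no new data and changes no dosing rule.
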